## **10 Statistical Considerations**

### **10.1 Statistical and Analytical Plans (SAP)**

A formal SAP will not be completed for this study.

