## 10.4 Description of Statistical Methods

### 10.4.1 General Approach

Data Analysis will be performed using SAS 9.4. We will perform statistical tests to examine baseline differences between the quality improvement program and control groups. We will then perform unadjusted comparison of both primary outcomes (patient and caregiver quality of life, emergency room visits) and secondary outcomes (pain, BPSD, delirium, caregiver depression burden, and burnout, hospital and emergency room admissions) between groups. We will focus on the endpoint measure for quality of life, and 30 and 60-day outcomes for emergency room utilization. For primary and secondary outcomes, we will perform a time trend analysis using a mixed effects linear model (PROC MCM). Mixed effects regression is used to analyze longitudinal data with repeated measures accounting for intra-individual and group clustering. We intend to use multivariate mixed effects regression modeling as opposed to traditional linear modeling or ANOVA in order to control for unobservable confounding variables that are constant over time but differ across PWD and/or caregivers. For both primary and secondary outcomes, we will then repeat the above analyses adjusting for baseline variables as covariates for a more efficient measurement of the effects of the quality improvement program. We will also perform correlation analyses to explore the relationship between pain and BPSD, and PWD and caregiver QOL through plotting scores over time and then if a significant correlation is present through adding to our mixed effect model. For utilization data, we will perform logistic regression to examine whether the patient is more or less likely to have a hospitalization or ER visit compared when receiving the quality improvement program at 30 and 60 days. We will then perform a Poisson Count Regression to compare the total number of hospitalizations and ER visits at each timepoint. In these models we will utilize a random effect to measure for clustering.

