### 10.4.2 Safety Analyses

We will perform interim analyses using descriptive statistics and two-sided t-tests, monitoring for a significance of 0.05 starting at the end of year 1 of the grant for safety purposes. These results will be presented unblinded to the DSMB.

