## 10.5 Sample Size

Power analyses were conducted using Optimal Design software. Given that this study is randomized at the cluster level, we must control for intra-class correlation, and have therefore calculated all power with an intra-class coefficient of .05, which is more conservative than the most recent clustered palliative care study and aligns well with prior community-based cluster trials. The Quality of Life in Alzheimer's Disease as the primary outcome measure in aim 1 has an average score of 33.1, standard deviation of 5.9. A .5 standard deviation difference in this measure would be clinically meaningful. Therefore, in a 2-sample comparison with a power of .80, an alpha of .05 and covariates that account for a cumulative 15% of the variance in outcome would require 15 dyads per cluster, and 20 clusters (10 per arm) at 60 days to detect a medium effect ( $\delta = .45$ ). For mixed effects linear models, the projected sample size will also allow us to detect a medium linear treatment effect ( $\delta = .45$ ) between groups in unadjusted analyses (assuming 15 dyads per cluster, 20 clusters, 4 observations, and an ICC = .05). Although there are no closed-form equations for calculating the power of linear models that include covariates, any non-zero correlation between covariates and the outcome will reduce the unexplained (error) variance thus increasing the statistical power of our tests, and reducing the minimum detectable effect size. As such, the detectable effect size estimated for the unadjusted analyses can be considered an upper bound estimate for the effect size detectable in adjusted analyses. **We will recruit until we have reached 15 completed cases in each cluster (N=300).** Conservatively anticipating a 15% dropout over the 60 days requires a **total recruitment goal of 345 dyads**. As almost 20,000 patients are seen each year in the three HHC agencies in this study, approximately 30% with ADRD, we do not expect any difficulty recruiting this sample, even with an unanticipatedly high rate of dyads declining to participate.

In addition, for fidelity monitoring, as discussed in section [6.1.6.1](#), we will consent **300 clinicians** at the participating HHC agencies on usual care and quality improvement care teams to complete fidelity monitor by performing the DSKA survey. These clinicians are not study subjects but will be consented as they are

CONFIDENTIAL

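### For QOL-AD and CGQOL, section 10.4.1 lists at least four analyses per endpoint, names none as deciding, and does not say whether the baseline QOL score is a covariate

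*Combined protocol and SAP*

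**What the plan says.** Section 10.4.1 sets out the QOL analyses in sequence: an unadjusted comparison between arms, a time trend from a mixed-effects linear model, and then "we will then repeat the above analyses adjusting for baseline variables as covariates for a more efficient measurement". The repeat covers both earlier analyses, so each QOL endpoint has at least four results. The baseline variables are not listed. On timing, the section says "We will focus on the endpoint measure for quality of life".

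Other sections lean in different directions:

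- The Protocol Summary names only the time-trend mixed model for all non-utilization outcomes.
- Section 4.2.1 frames a positive QOL result as a 0.5 SD difference between baseline and day 60.
- Section 10.5 first powers a two-arm comparison with covariates "at 60 days to detect a medium effect". It then powers an unadjusted mixed model with four observations per dyad.
- The visit lists in section 7.2 and Table 2 schedule QOL-AD and CGQOL at days 0 and 60 only.

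Nothing else settles the choice. Section 10.1 says "A formal SAP will not be completed for this study", and section 10.4.7 marks multiplicity as not applicable.

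**The concern.** With several correlated tests of the same endpoint and no stated order among them, the reader of the final report cannot know which p-value was meant to settle Aim 1 or Aim 2. The risk is practical. Section 8.8.1 has the statistician run quarterly reports that include outcomes and review them with the PI, and sections 4.1 and 10.6.1 show that both know the allocation. The protocol does not say whether those reports are split by arm.

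The second issue is efficiency. Section 10.4.1 itself says that covariate adjustment is more efficient, yet places it third, as a repeat. The variable most likely to help, the day-0 value of the same score, is already collected but never named as a covariate. The unadjusted day-60 comparison ignores it. The two-visit trend uses it as a repeated response, which amounts to comparing change scores when the two arms' baseline means are estimated freely.

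**Working it through.** **Inputs from section 10.5.** 20 care teams (10 per arm), 15 dyads per team, ICC .05, delta .45 SD, "with a power of .80, an alpha of .05". QOL-AD "has an average score of 33.1, standard deviation of 5.9", so .45 SD is .45 × 5.9 = 2.66 points. Sidedness is not stated for the primary tests. The only mention is for the interim looks (section 10.4.2: "descriptive statistics and two-sided t-tests, monitoring for a significance of 0.05"), so two-sided is assumed.

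**Assumption.** The correlation r between baseline and day-60 QOL is not in the documents. I take .3 to .8 and the same r at team and dyad level.

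**Step 1: the plan's own figure.** Variance of a team mean in SD units: .05 + .95/15 = .1133. Noncentrality: 20 × .45² / (4 × .1133) = 4.05/.4533 = 8.93. A noncentral F test on 1 and 18 df gives power .807, with a minimum detectable effect of .446. This reproduces the planned .80 at delta .45. The match is to the calculation without covariates; the stated 15% covariate share would give .83 (team level only) to .86 (both levels).

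**Step 2: power of each candidate.** Multiply the variance by 1 for unadjusted day 60, by 2(1 − r) for the change or two-visit trend with free baseline arm means, and by 1 − r² for adjustment on baseline QOL (17 df). For example, at r = .3 the noncentrality is 8.93/1.40 = 6.38 for change and 8.93/.91 = 9.81 for baseline-adjusted.

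| r (assumed) | Unadjusted day 60 | Two-visit trend | Baseline-adjusted |
|---|---|---|---|
| .3 | .807 | .666 | .839 |
| .5 | .807 | .807 | .902 |
| .7 | .807 | .954 | .976 |

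The one related figure in the protocol is the 15% of variance attributed to covariates. If baseline QOL alone supplied it, r = √.15 = .387, and power would be .863 adjusted, .807 unadjusted and .724 for the trend.

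**Step 3: type I error if any result may be claimed.** 100,000 null trials were simulated per r on team means, each test done correctly at team level. Each test alone rejected in 4.9 to 5.1%. At least one of the three (unadjusted day 60, change, baseline-adjusted) rejected in 9.2% (r = .3), 9.5% (.5), 9.8% (.6), 10.0% (.7) and 10.1% (.8). Counting only results that favour the program, the figures are 4.6 to 5.1% against a nominal 2.5%. If only the unadjusted and baseline-adjusted day-60 results compete, the two-sided figure is 6.6 to 8.6%. The adjusted trend, a further result under the plan, is not in this calculation because its covariates are unknown.

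**The case against.** The best defence is that the protocol does show a preference. The Protocol Summary names only the mixed model, and section 10.4.1 explains why mixed-effects regression is preferred to ordinary linear modelling or ANOVA. That points to a model family. It leaves open whether the adjusted or unadjusted version decides, and it does not sit easily with the day-60 comparison that section 10.5 powers first.

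Several stronger readings are tempting, and the documents do not support them:

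- A reader might infer that the unadjusted day-60 test is the lead analysis. The sentence on the endpoint measure also covers the 30- and 60-day utilization outcomes. It chooses time points, not a test.
- A reader might infer that baseline QOL is left out of the main analyses. The time trend uses the day-0 score as a response; what is missing is its use as a named covariate.
- A reader might infer that the adjusted repeat excludes baseline QOL because section 10.4.4 does not list it. That list concerns baseline comparisons and is not exhaustive. The covariate set is unspecified, not known to omit QOL.
- A reader might infer that the trial is underpowered. Unadjusted day 60 still meets the planned .80, and the trend falls below it only when r is under .5.

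It is also fair to say that adjusting the day-60 score for baseline is not the only efficient choice. A mixed model with baseline means constrained equal across arms would serve equally well and would fit the stated preference.

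**Conclusion.** The point stands as a gap in specification with a cheap efficiency gain attached. For each QOL primary there are at least four planned results and no rule for which one decides. The Protocol Summary and sections 4.2.1, 10.4.1 and 10.5 do not agree, and the four-observation model in section 10.5 does not describe outcomes measured twice.

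A reader might conclude that the plan doubles the error rate. That holds only if success may be declared on whichever of the three results is significant. No section states such a rule, but none excludes it.

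The power figures are relative to the baseline-adjusted analysis and rest on an assumed r. Across r of .3 to .7, naming baseline QOL as a covariate gains about 3 to 17 points over unadjusted day 60, and about 17 down to 2 points over the trend with free baseline arm means. It has the highest power at every r examined, so the direction of the advice does not depend on the assumption; its size does.

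**What to change.** In section 10.4.1, name one deciding analysis for QOL-AD and one for CGQOL: day-60 score on arm, with the baseline value of the same score as covariate, the randomization strata (agency and geographic location), and a care-team random effect. An equivalent mixed model with baseline means constrained equal across arms is also acceptable. Label the unadjusted and time-trend results as supportive.

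Then align the rest of the protocol: the statistical analysis entry in the Protocol Summary; the success statement in section 4.2.1, so that it describes the contrast actually tested; and section 10.5, including the four observations. Make the change before anyone examines outcomes by arm for the final report.

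The cost is a few wording edits. Both scores are already collected. The sponsor gives up the freedom to choose among results, and type I error is held at 5% for each QOL endpoint.

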## **4 Study Design and Endpoints**

### **4.1 Description of Study Design**

This study will use a blinded cluster randomized controlled trial methodology. Each HHC care team will be randomized to either partake in the DSM-H performance improvement program or provide usual care. The project director based at NYU and RAs at all sites will be blinded to prevent bias in data collection. The study statistician based at NYU will perform the randomization utilizing SAS 9.4 stratified by agency and geographic location. The study PI will relay to the agencies which teams will serve as intervention or control. The study PI and statistician will not collect study data in order to maintain the integrity of the blinding. The potential for contamination between care teams randomized to receive the DSM-H performance improvement program and those who will provide usual care is minimal due to the nature of HHC clinician workflow where minimal time is spent in the office, and different care teams do not generally congregate with each other except during highly structured staff meetings. The investigators considered randomizing by site and using other HHC agencies; however, given the lack of contamination found in prior studies of the DSM-H combined with differences in care provision at other sites/locations and the need for a large number of clusters when using this methodology, the investigators felt this method was the most likely to provide valid and reliable results. It is not possible to randomize by patient in HHC because patients are seen by care teams in a given geographic region. Patients in the performance improvement group will receive care from a care team who has received the DSM-H performance improvement program, and those in the control will receive usual care from a care team who has not received the performance improvement program. Patients at the study sites are only cared for by members of the same care team and therefore there is no potential for patients to receive a mixture of care teams.

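### The time-trend model names no team-by-time term; if it is fitted with person and team intercepts only, its arm-by-time test does not reflect team variation in change

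*Combined protocol and SAP*

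**What the plan says.** Section 4.1 sets the unit of randomisation: "Each HHC care team will be randomized to either partake in the DSM-H performance improvement program or provide usual care". For primary and secondary outcomes, Section 10.4.1 states that "we will perform a time trend analysis using a mixed effects linear model (PROC MCM"), and describes the method in one sentence: "Mixed effects regression is used to analyze longitudinal data with repeated measures accounting for intra-individual and group clustering". It does not define the group level, say whether the random effects are intercepts or slopes, or give a degrees-of-freedom method. A random effect for clustering is mentioned again only for the logistic and Poisson utilisation models: "In these models we will utilize a random effect to measure for clustering".

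The same section also says "We will focus on the endpoint measure for quality of life, and 30 and 60-day outcomes for emergency room utilization". In the schedule of Section 7.2 and in Table 2, the two quality-of-life instruments are given at days 0 and 60 only. NPI-Q and pain are collected at days 0, 15, 30 and 60.

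Section 10.5 opens with "Given that this study is randomized at the cluster level, we must control for intra-class correlation", and the authors "have therefore calculated all power with an intra-class coefficient of .05". That single ICC is used both for the 60-day comparison and for the four-observation mixed model. Section 10.1 says that no formal SAP will be written, so nothing else in the documents settles the random structure.

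**The concern.** A time-trend comparison between arms is a test of arm by time. In a team-randomised trial, that test is threatened by teams differing in how much their patients change. A random intercept for team describes a difference that is the same at every visit, so it drops out of any change over time. A model with person and team intercepts therefore appears to handle clustering while the contrast being tested is treated as if dyads had been randomised individually.

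Two features of the text make intercepts the natural reading. Section 10.4.1 justifies the model by unmeasured factors that do not vary with time but differ between persons, and Section 10.5 supplies one ICC and no variance for team trends. The design also gives a reason to expect teams to diverge: Section 7.2.1 places visit 1 within three business days of start of care, before the team has had much influence, whereas day 60 follows a full certification period. At stake are intervals that are too narrow and too many false positives in the trend analyses.

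**Working it through.** **Inputs from the documents.** J = 20 teams (10 per arm), n = 15 dyads per team, ICC ρ = .05, α = .05, δ = .45 (Section 10.5). Two-sided testing is assumed.

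**Inputs assumed.** c is the correlation of a team's effect between visits; r is the correlation of a person's scores within a team. Neither is in the documents.

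**1. The plan's own figure.** For a day-60 comparison without covariates, SE = √(4[ρ + (1−ρ)/n]/J) = √(4[.05 + .95/15]/20) = 0.1506 SD. Then δ/SE = .45/.1506 = 2.99, and the noncentral t with 18 df gives power 0.807. The detectable difference at 80% power is 0.446. The stated .45 is reproduced, for a contrast that does contain team variance.

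**2. Cancellation.** Write a score as fixed effects + team intercept + person intercept + residual. Subtracting day 0 from day 60 removes both intercepts. In one balanced simulated data set (20 × 15, two visits, large team variance), the SE of arm by time was 0.0997 without a team intercept, 0.0997 with one, and 0.0997 from a t-test on change that ignores team. The SE of the arm main effect rose from 0.124 to 0.250, so the team term was active, but not in the trend contrast.

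**3. Size of the intercept-only test.**

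- ICC of change = ρ(1−c) / [ρ(1−c) + (1−ρ)(1−r)]
- Design effect D = 1 + 14 × ICC of change
- Type I error = 2[1 − Φ(1.96/√D)]
- SE understated by 1 − 1/√D

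For example, with c = .8 and r = .5 the ICC of change is .010/(.010 + .475) = .0206, D = 1.29, and the size is 8.4%.

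| c | r | ICC of change | D | SE understated | Type I error |
|---|---|---|---|---|---|
| 1 | any | 0 | 1.00 | 0% | 5.0% |
| .8 | .5 | .0206 | 1.29 | 12% | 8.4% |
| .8 | .7 | .0339 | 1.47 | 18% | 10.7% |
| .5 | .5 | .0500 | 1.70 | 23% | 13.3% |
| .5 | .7 | .0806 | 2.13 | 31% | 17.9% |
| .5 | .8 | .1163 | 2.63 | 38% | 22.7% |

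The fourth row is also the answer if the plan's ICC of .05 is applied to change itself.

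**4. Simulation.** With 20,000 trials per setting, the c = .8, r = .5 and c = .5, r = .7 cases gave 8.4% and 18.1% to 18.6% for visits at days 0 and 60. For visits at days 0, 15, 30 and 60 they gave 8.3% to 8.5% and 17.5% to 18.2%. The ranges cover team variation by visit and as a linear slope. A test on team-level changes or slopes with 18 df held 4.7% to 5.4% in all settings.

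**5. Degrees of freedom.** A correct team-level statistic compared with 1.96 instead of the t cutoff on 18 df has size of about 6.6%, so the variance term and the df rule are both needed.

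**The case against.** The plan never says intercept only. It does not exclude a team slope, it names group clustering for the mixed model, and it carries ICC .05 into that model's power statement, which shows an intention to allow for teams. A reader might infer that the trend test as planned ignores care teams and runs at a known rate well above 5%. The documents do not support that: the random structure is unspecified, and the inflation depends on correlations that they do not give. Part of the difference between teams may well be stable, because Section 10.6.1 assigns patients to teams by geographic area. At c = 1 there is no inflation at all.

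A reader might also infer that both quality-of-life primaries are compromised. That does not follow either. Section 10.4.1 puts the focus for quality of life on the endpoint measure, the hypotheses in Section 10.2 refer to the end of the 60-day period, and a team intercept does act in a day-60 contrast. This part of the objection stands, with one limit: the text names no cluster term for its unadjusted group comparisons. The trend model also remains a listed analysis of these outcomes, since the Protocol Summary assigns it to everything except utilisation.

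What the objection does not remove is the gap. The wording most easily leads an analyst to person and team intercepts, and no later document will correct that.

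**Conclusion.** The point holds in conditional form. The random structure of the trend model is not stated. If it is fitted with person and team intercepts, the arm-by-time test contains no term for team variation in change. Its type I error is then 5% with constant team effects, 8.4% to 17.9% for c of .5 to .8 and r of .5 to .7 at ICC .05, 13.3% if ICC .05 applies to change, and 22.7% at c = .5, r = .8. These figures assume 20 equal teams of 15, complete data and two-sided testing. The existence of the gap rests on the text; its size rests on assumed correlations. The four-visit outcomes (NPI-Q, pain) are the most exposed. The day-60 quality-of-life comparison is not affected provided it carries a team random effect. The model should be fixed in writing before analysis.

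**What to change.** In Section 10.4.1:

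- **Quality-of-life primaries (two visits).** Analyse the day-60 score with the day-0 score as covariate and a random team intercept, using between-team degrees of freedom (about 18, from 20 teams less 2 arms).
- **Four-visit trend models.** Beside the team and person intercepts, add a team-by-time random term: a team-by-visit effect if visit is categorical, or a team random slope if time is linear. These are different models at four visits, so the text should say which applies. Use between-team degrees of freedom here too.

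This takes a few lines of specification and no new data. The price is somewhat wider intervals: in the trend models the SE rises by √D, a factor of 1.14 to 1.46 across the c = .5 to .8, r = .5 to .7 range, and hardly at all if team effects are constant. For the day-60 comparison there is no loss against Section 10.5, whose stated power is reproduced above with team variance and 18 df already included.
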